8.4. Data Handling

For adverse events (AEs), handling rules for partial onset and resolution dates are detailed in Section 8.4.2. For the other safety data, unless otherwise stated, only observed data will be used for analyses.

8.4.1. Handling of Repeated and Unscheduled Assessments

In general, for by-visit summaries, data recorded within analysis visit window will be presented. The visit mapping rule is described in Section 8.3. Results that cannot be mapped will not be included in the by-visit summaries however will contribute to the best/worst case value and last on-treatment visit, where applicable.

Tumor assessments at unscheduled visits may be used for the derivation of the primary endpoint and other efficacy endpoints based on visit windows.

The repeated and unscheduled measurements will be presented in the listings.

8.4.2. Handling of Partial Dates for Adverse Events

For AEs with partial or missing start or stop dates, the following imputation approach will be used.

Partial start date:

- If the day of the month is missing, the onset day will be imputed as the first day of the month unless it is the same month and year as the start of study treatment. In this case, the onset date will be imputed as the first dose date of study treatment.
- If the onset day and month are both missing, the day and month will be imputed as January 1, unless the event occurred in the same year as the start of study treatment. In this case, the event onset will be imputed as the first dose date of study treatment to conservatively report the event as treatment emergent.
- A missing onset date will be imputed as the first dose date of study treatment. If the resulting onset date is after a reported date of resolution (AE end date), the onset date will be imputed as the date of resolution.

Partial end date:

- If the day of the month is missing, the end day will be imputed as the last day of the month or death date or data cut-off date (or end of study date), whichever is earliest.
- If the end day and month are both missing, the day and month will be imputed as December 31 or death date or data cut-off date (or end of study date), whichever is earliest.
- A missing end date will be left as missing if the event is ongoing. Otherwise, it will be imputed as the death date or data cut-off date (or end of study date), whichever is earliest.

Imputation of missing or partial dates for adverse events is used only to determine whether an event is treatment-emergent and calculation of duration of adverse events; data listings will present the missing or partial date as recorded in the eCRF.

In the event of a partial date for date of death, imputation will follow the approach described above for AE start date, unless there is an existing date of last contact later than the imputed date, in which case the date of death would be imputed as the day after the date of last contact.

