9. STUDY DRUG MATERIALS AND MANAGEMENT

9.1. Study Drug

Information regarding study drug are summarized in Table 7. In this protocol, study drug will refer to vimseltinib and placebo.

Vimseltinib (DCC-3014) will be provided as 2 mg and 10 mg capsules for oral administration.

Placebo will be supplied as identically sized and color-matched capsules.

Study Arm	Vimseltinib	Placebo
Intervention Name	Vimseltinib	Placebo
Dose Formulation	Capsule	Capsule
Unit Dose Strengths	2 mg, 10 mg	Matching placebo
Dosage Level	30 mg biw	Same frequency as vimseltinib
Route of Administration	Oral	Oral
Physical Description	Size 4, hard gelatin capsules: 2 mg (blue) and 10 mg (white)	Identically sized and color-matched capsules
Use	Experimental	Placebo comparator
IMP/NIMP	IMP	IMP
Sourcing	Provided centrally by the Sponsor	Provided centrally by the Sponsor
Packaging and Labeling	Vimseltinib will be provided in 30-count high density polyethylene bottles with an induction seal/child-resistant closure. Each bottle will be labeled as required per country regulations.	Identically packaged as active drug. Each bottle will be labeled as required per country regulations.

Table 7:Study Drugs

Abbreviations: biw=twice weekly; IMP=investigational medicinal product; NIMP=non-investigational medical product.

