9.11. Safety Analysis

All safety analyses will be conducted on the SAF. If there are both local and central assessments in the same nominal visit, then the central assessment will be used for analyses. The safety data will be summarized following two different approaches. The first approach will be limited to data from Part 1 and will focus on comparisons between participants who received vimseltinib versus participants who received placebo during this period. The second approach will combine data from both Part 1 and Part 2 (including extension period) and will focus on the observations and assessments while participants are receiving vimseltinib. Therefore, in this second approach, participants randomized to Placebo in Part 1 who crossed over to vimseltinib in Part 2, will have as their reference day the first dose date of vimseltinib in Part 2, and their data from Part 1 while receiving placebo will be excluded.

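### Incomplete AE onset dates in crossover participants can be imputed to before the first vimseltinib dose, so possible vimseltinib events drop out of the combined on-vimseltinib safety summary

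*SAP*

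**What the plan says.** SAP 8.4.2 gives three rules for AE onset dates.

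- No day recorded: "the onset day will be imputed as the first day of the month unless it is the same month and year" in which treatment began; a match gives the first dose date.
- Only the year recorded: "the day and month will be imputed as January 1, unless the event occurred in the same year as the start of study treatment"; when it did, the first dose date is again used. The stated purpose is "to conservatively report the event as treatment emergent".
- Date fully missing: "A missing onset date will be imputed as the first dose date of study treatment". If that falls after a reported resolution date, the resolution date is used instead.

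The section adds that imputation "is used only to determine whether an event is treatment-emergent and calculation of duration of adverse events". Listings keep the date as recorded.

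No rule mentions crossover. Protocol 9.1 states: "In this protocol, study drug will refer to vimseltinib and placebo". SAP 7.4 uses study treatment in the same sense, since the Safety Set covers everyone who received a dose of either.

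SAP 9.11 plans two safety summaries. The first is limited to Part 1 and compares vimseltinib with placebo. The second combines Parts 1 and 2 for time on vimseltinib. In it, crossover participants take the first vimseltinib dose as their reference day, and "their data from Part 1 while receiving placebo will be excluded".

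**The concern.** The rules are written for a participant who receives one treatment. In that setting, pulling an uncertain onset back to the first dose is conservative, because it makes the event treatment-emergent. For a participant who takes placebo for 24 weeks and then vimseltinib, the same step places the event in placebo time. An AE that may have begun on vimseltinib is then excluded from the summary meant to describe vimseltinib safety, which reverses the section's stated intent.

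The gap is specific to AE dates. The SAP re-anchors crossover participants for baseline (8.1), for duration of response after crossover (9.10.4.3), for exploratory efficacy over time (9.10.7) and for the safety reference day (9.11). Protocol 12.5 leaves date algorithms to the SAP, so no other text supplies the rule.

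**Working it through.** The plan gives no figure on this point, so there is none to reproduce. The check applies the rules as written.

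**Inputs from the documents.** Part 1 lasts 24 weeks, or 168 days (SAP 2). About 80 participants are randomized to vimseltinib and 40 to placebo (SAP 5). A participant counts once per preferred term (SAP 9.11.2).

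**Assumptions.** Crossover is exactly 168 days after the first placebo dose. True onset is uniform over the first 24, 48 or 72 weeks on vimseltinib. The placebo start is equally likely on each of the 365 days of 2022. No end date precedes the imputed onset.

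**Step 1: worked cases.** Placebo starts 10 February 2022, so the first vimseltinib dose is 168 days later, on 28 July 2022.

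- True onset 5 September 2022, undated or year-only: imputed to 10 February, in the placebo period.
- The same onset with only the day missing: imputed to 1 September, correctly on vimseltinib.
- True onset 30 July 2022 with the day missing: imputed to 1 July, in the placebo period.
- True onset 1 February 2023, year only: imputed to 1 January 2023, correctly on vimseltinib.

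The 1 January rule misplaces events when crossover falls in the calendar year after the start. With placebo from 10 October 2022, the first vimseltinib dose is 27 March 2023. A year-only 2023 onset goes to 1 January 2023, in the placebo period.

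**Step 2: share of true vimseltinib-onset events dated to placebo.** For each start date and each onset day: share = (number of onset days whose imputed date is before the first vimseltinib dose) / (all onset days).

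| Onset date recorded | 24 weeks | 48 weeks | 72 weeks |
|---|---|---|---|
| Nothing | 100% | 100% | 100% |
| Year only | 76.8% | 53.8% | 36.1% |
| Month and year | 8.8% | 4.4% | 2.9% |

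In the same enumeration, no true placebo-onset event is moved onto vimseltinib. The error in the combined summary therefore runs one way.

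**Step 3: size in the combined summary.** If everyone on placebo crosses over, the denominator is 80 + 40 = 120. Each participant whose only record of a term is lost lowers that term's rate by 1/120 = 0.83 points. If 0 to 5 participants per term are affected (an assumption), the loss is 0 to 5/120 = 4.2 points.

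**Step 4: the Part 1 comparison.** A vimseltinib-arm participant who continues into Part 2 also has the Part 1 first dose as anchor. An undated Part 2 event is therefore pulled back into Part 1 in either arm. One such event adds at most 1/40 = 2.5 points on placebo or 1/80 = 1.25 points on vimseltinib, and nothing if the participant already has that term in Part 1. As an illustration, suppose 5% of each arm has one such event. The additions are 2/40 = 5 points and 4/80 = 5 points, so the difference does not change.

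**Step 5: re-anchoring to the first vimseltinib dose.** The share of vimseltinib-onset events lost falls to 0% in every row. The reverse error appears: 100% of undated, 76.8% of year-only and 8.8% of day-missing true placebo-onset events move to vimseltinib, unless an end date or visit record places them earlier.

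**The case against.** **The reset reference day in SAP 9.11 may already solve it.** If the first vimseltinib dose also anchors imputation for the combined summary, nothing is lost there. That reading is possible, but the text does not say that dates are re-imputed. Under it, the same event could count both as a Part 1 placebo event and as an on-vimseltinib event. The ambiguity is reason enough to write the rule down.

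**Imputed dates settle only emergence and duration, not treatment period.** That is what SAP 8.4.2 says. But once the reference day is the first vimseltinib dose, being emergent relative to that day is what decides inclusion. If imputed dates do not decide the period, no stated rule does.

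**The randomized comparison.** A reader might infer that the rules also favour vimseltinib in Part 1 by inflating placebo rates. The documents do not support this. The same rules apply to continuing vimseltinib participants, and the net direction depends on Part 2 event rates and earlier Part 1 counts, which are not given. This objection stands in full. It also means that a crossover-only rule applied to Part 1 would itself treat the arms differently: in the 5% illustration, placebo would gain 0 points and vimseltinib 5.

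**Few events are exposed.** AE review takes place while blinded at the End of Part 1 visit (Protocol 11.5.1), AEs are collected continuously, and listings show recorded dates. This limits the size but does not remove the problem, because clinic visits in the extension are 12 weeks apart (Protocol Tables 2 and 3).

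**Conclusion.** The point holds for the combined on-vimseltinib summary. Followed as written, SAP 8.4.2 with 9.11 removes some AEs that began on vimseltinib, and the error there can only understate vimseltinib incidence. Undated and year-only onsets are the main route. The shares rest on uniform onset and a 168-day crossover. The effect on any rate depends on a count of incomplete dates that the documents do not give, among at most about 40 participants.

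Two broader readings do not hold. One is that every partial date goes to the first dose: most day-missing dates go to the first of their month and later-year dates to 1 January, so those misplace events mainly in the crossover month or year. The other is that about half of day-missing events are misplaced. On average 465/900 = 51.7% of a 30-day crossover month lies on or after the crossover day, but that covers one month only. Over follow-up the day-missing share is 9% or less.

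In Part 1, events can be misallocated in both arms, with no established direction.

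**What to change.** Add two rules to SAP 8.4.2.

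(a) For the combined on-vimseltinib summary: if a crossover participant's partial or missing onset date is compatible with onset on or after the first vimseltinib dose, and no end date or earlier visit record places it before, impute onset as the first vimseltinib dose date. Dates whose known parts already lie wholly after that dose can keep the existing rules.

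(b) For the Part 1 comparison, in both arms alike: an event with an incomplete date that is first recorded after the End of Part 1 AE review, and whose known date parts and end date are compatible with Part 2 onset, is assigned to Part 2.

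The cost is a short SAP addition and a few lines of programming, using the visit at which each AE was first recorded. The downside is that some events that truly began in Part 1 will be assigned to vimseltinib or to Part 2. The reverse shares in step 5 are the upper end of that error, before end dates and visit records are used. For the combined summary, that error is conservative for the drug under test.

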8.4.3. Handling of Partial Dates for Original Diagnosis

For original diagnosis with partial or missing dates:

- No imputation will be done if the year is missing
- If the year is before the informed consent date, the missing day will be imputed as the first day of the month and missing month will be imputed as July
- If the year is the current year of informed consent date, the missing day will be imputed as first day of the month and missing month will be imputed as January

8.4.4. Handling of Partial Dates for Medications

When determining prior or concomitant medications, partial start dates of prior and concomitant medications will be assumed to be the earliest possible date consistent with the partial date.

- Medication start dates with a missing day and non-missing month and year will be imputed as the first day of the non-missing month, except for medications with a start date in the same month and year as the first dose of study treatment, in which case the start date will be imputed as the first dose date.
- Medication start dates with missing day and month and non-missing year will be imputed as the first day of the non-missing year (i.e., 01 January), except for medications with a start date in the same year as the first dose of study treatment, in which case the start date will be imputed as the first dose date.
- A missing medication start date will be imputed as the first dose date.
- Medications that are not ongoing and have a medication stop date with a missing day
 and non-missing month and year will have their stop date imputed as the last day of
 the non-missing month, except for medications with a stop date in the same month
 and year as the last study date, in which case the stop date will be imputed as the last
 study date.
- Medications that are not ongoing and have a medication stop date with missing day
 and month and non-missing year will have their stop date imputed as the last day of
 the non-missing year (i.e., 31 December), except for medications with a stop date in
 the same year as the last study date, in which case the stop date will be imputed as the
 last study date.

Imputation of missing or partial dates for medications is used only to determine whether a medication is a prior or concomitant medication. Data listings will present the missing or partial date as recorded in the eCRF.

8.4.5. Handling Partial Dates for Non-drug Therapy/Procedure

Imputation of missing or partial dates for non-drug therapy/procedure will follow the same approach as will be used for medications. This imputation will be used only to determine

whether a therapy/procedure is prior or concomitant therapy/procedure. Data listings will present the missing or partial date as recorded in the eCRF.

9. STATISTICAL CONSIDERATIONS

All analyses described in this plan are considered a priori analyses in that they have been defined prior to locking the database. All other analyses, if any, designed subsequently to locking the database, will be considered post hoc analyses and will be described as exploratory analyses in the clinical study report (CSR) or a separate document.

All summaries and statistical analysis will be performed using SAS v9.4 or higher.

9.1. General Methods

Data collected in this study will be documented using summary tables and participant data listings. Continuous variables will be summarized using descriptive statistics (number of observations, mean, median, standard deviation, minimum, and maximum). Categorical variables will be summarized using frequencies and proportions. Time-to-event data will be summarized via Kaplan-Meier (KM) methodology using the 25th, 50th (median), and 75th percentiles with associated 2-sided 95% confidence intervals (CIs).

Medical history, AEs, and concurrent procedures will be coded using Medical Dictionary for Regulatory Activities (MedDRA) version 26.0 (or higher). Prior and concomitant medications will be coded using the World Health Organization (WHO) Drug Dictionary March 2023 Global B3 or later.

This study comprises 2 periods: the randomized double-blinded period (Part 1) and the open-label portion that occurs after unblinding the study treatment at Week 25 (or earlier if there is a treatment discontinuation due to a centrally confirmed disease progression) (Part 2).

Unless otherwise specified, the ITT and PP Sets are used for efficacy analysis and the SAF is used for the safety analysis.

The primary analysis will be conducted at the earliest when all participants have completed the double blinded treatment period (Part 1).

In general, unless otherwise specified, data summaries will be presented by treatment group (vimseltinib versus placebo) and overall. Between-group comparisons will focus on the comparative performance of vimseltinib versus placebo. All statistical tests will be conducted at a 2-sided significance level of 0.05.

9.2. Participant Disposition

The number and percentage of participants achieving some planned assessment listed below will be summarized by treatment group and overall (if applicable):

- Summary of randomization by country and site
- Summary of randomization stratification
- Summary of analysis sets (ITT, PP, SAF, PK, PRO)

- Participant disposition:
 - o Screened
 - Randomized
 - Treated
 - Entered double-blinded treatment phase (Part 1)
 - Discontinued double-blinded treatment
 - Reason for discontinuation of treatment
 - Completed Part 1 treatment
 - Discontinued study during Part 1
 - Reason for discontinuation of study
 - Entered open label phase (Part 2) (received at least one dose of study treatment in Part 2)
 - Ongoing on treatment
 - Discontinued open label phase treatment
 - o Reason for discontinuation of treatment
 - Discontinued study during Part 2
 - Reason for discontinuation of study
 - Discontinued from treatment
 - Reasons for discontinuation of treatment
 - Discontinued from study
 - Reason for study discontinuation

Listings will be provided for screen failures, as well as treatment and study discontinuations.

9.3. Protocol Deviations

A protocol deviation is any change, divergence, or departure from the study design or procedures defined in the clinical protocol. All protocol deviations will be reviewed and documented before database lock.

Protocol deviations will be classified as major or minor by medical review prior to the primary analysis. Major protocol deviations will be identified as those deviations from the study protocol that may significantly impact the completeness, accuracy, and/or reliability of the trial data; that may significantly affect a participant's rights, safety, or well-being. A subset of major protocol deviations referred to as IPDs will also be identified prior to the primary analysis. IPDs will be pre-specified in a separate document, they will consist of major protocol deviations resulting in the exclusion from the PP Set because they may affect efficacy. The number and percentage of participants with major deviations and IPDs will be tabulated for the ITT Set.

All protocol deviations will be listed for the ITT Set.

9.4. Demographics and Baseline Characteristics

Demographics and baseline characteristics will be summarized descriptively by randomized treatment assignment for the ITT Analysis Set. They will also be summarized by actual treatment received for the SAF and PP Set. The following variables will be included in the summary table:

- Age (years)
- Age category $(18 \le age < 50, 50 \le age < 65, 65 \le age < 75, 75 \le age < 85, age \ge 85)$
- Sex (Male vs Female)
- Childbearing potential (Yes vs No)
- Race
- Ethnicity
- Baseline Weight (kg)
- Baseline Height (cm)
- Body Mass Index (BMI, kg/m²)
- BMI Interpretation (underweight [<18.5], normal [18.5 <25.0], overweight [25.0 <30.0], obese [≥ 30.0])
- Tumor location (lower limb vs all other)
- Region (U.S. vs non-U.S.)
- Baseline narcotic use (Yes vs No)

Demographics and baseline characteristics will be listed for the ITT population.

9.5. Disease History

Participants' disease history will be summarized for ITT and SAF including:

- Time from original diagnosis to first dose date (years), calculated as (First dose date original histopathological diagnosis date)/365.25
- Disease subtype
- Primary affected joint

Disease history listing will be provided for the SAF.

9.6. Prior TGCT Therapies and Procedures

Prior therapies and procedures will be tabulated for ITT and SAF including:

- Any prior surgery
- Any prior radiation therapy
- Any systemic therapy
 - o Imatinib

- Nilotinib
- Other
- Best overall response to last therapy
- Reason for discontinuation of last therapy/procedure

Prior TGCT therapies and procedures will be listed for the SAF.

9.7. Prior and Concomitant Non-drug Therapy/Procedure

Prior non-drug therapies/procedures are defined as any non-drug therapies/procedures, with a stop date before the first dose of study drug.

Concomitant non-drug therapies/procedures are defined as any non-drug therapies/procedures, performed on or after the first dose of study drug and up to the end of study. Non-drug therapies/procedures that started before the first dose of study drug and were ongoing on the date of the first dose of study drug will be considered as both prior and concomitant non-drug therapies/procedures.

Prior and concomitant non-drug therapies/procedures will be coded using MedDRA version 26.0 (or higher) and will be summarized by system organ classifications (SOC) and preferred term (PT).

Prior and concomitant non-drug therapies/procedures will be listed for the SAF.

